Although each organ will receive a different dose, the maximum amount of radiation exposure subjects will receive per year from this study is equal to an effective dose equivalent of 2.4 rem for a total of 2 injection(s) of up to 20 mCi of [11C]CUMI-101 and 2 injection(s) of up to 20 mCi of [11C]DASB.

The amount of radiation subjects will receive in this study is below the dose guidelines established by the FDA and monitored by the Yale-New Haven Hospital Radiation Safety Committee for research subjects. This guideline sets an effective dose limit of 5 rem per year.

The dosimetry tables below provide the absorbed radiation dose calculation for [¹⁸F]MeFWAY based on a dosimetry studies in humans. ¹⁸⁷ [¹⁸F]MeFWAY dosimetry estimates ^{101,102} are shown in Table 4. By voiding the urinary bladder at 90 minutes, as recommended by a recent human [¹⁸F]MeFWAY dosimetry study, ¹⁸⁷the radiation dose is expected to be halved. By emptying the bladder at 90 minutes, the single study exposure to the critical organ (urinary bladder) with the minimum dose of 2.0 mCi and maximum dose of 2.5 mCi, as per Stony Brook RDRC protocol, results in radiation dosage of up to 1.9 Rad (Rem) for males and 2.46 Rad (Rem), which is under the 5 Rem single dose limit under the FDA 21 361.1.

For the maximum number of scans (3), the dose to the critical organ would be 5.7 Rad (Rem) for males and 7.38 Rad (Rem) for females, which is less than the 15 Rem annual dose limit under FDA 21 361.1. 22.8. It will be necessary to void the urinary bladder at 90 minutes. Each scan will be about 120 minutes or less, however, all participants will be required to void at 90 minutes. The scan will not continue if they cannot void their urinary bladder. We will encourage fluids including coffee, tea, and water intake. The half-life of \$\$^{1[8}F]MeFWAY\$ is 109 minutes and at least half of the radioactivity from the radiotracers, is expected to disappear by voiding the urinary bladder at 90 minutes. The rest of the tracer will be excreted through general dissipation and from urine from the body within 24 hours. Because the radiation dosage is close to the maximum annual radiation dose limit, we will ask about the participant's prior radiation exposure during the initial evaluation to ensure the radiation dose they are receiving from all research studies is less than the annual dose limit.

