Table 3 shows the absorbed radiation dose calculation for [\(^{11}\)C]CUMI-101 based on our human dosimetry data (MIRDOSE calculation based on baboon data). Similarly, Table 3 provides the absorbed radiation dose calculation for [\(^{11}\)C]DASB based on the dosimetry study of [\(^{11}\)C]DASB in humans (Lu et al., 2004). The critical

Stony Brook University Human Subjects Committee (IRB) PSF 2/23/15

Page 26 of 37

IRB# 2012-1826-F PI: [name]

organ is the testes in males and bladder wall in females for [11C]CUMI-101, and the lungs for [11C]DASB. The exposure after a single injection of [11C]CUMI-101 and [11C]DASB is below the single dose limit under the FDA 21 361 dose limits for research subjects (3 rem per injection, 5 rem annually for whole body, active blood forming organs, lens of the eye and gonads and 5 rem per injection, 15 rem annually for other organs).

Single Study Limit

[11C]CUMI-101: For the [11C]CUMI compound, the single study exposure to the critical organ (testes in males, bladder wall in females) with the maximum dose of 20 mCi, is 2.4 rem (males) and 1.5 rem (females) is below the 3(testes)/5(bladder wall) rem *single dose limit* under the FDA 21 361.1.

[11C]DASB: Table 3 provides the absorbed radiation dose calculation for [11C]DASB. The dose estimates indicate that the maximum permissible single study dosage of [11C]DASB in human subjects remain below the 21 CFR 361.1 dose limit for research subjects which is 20 mCi (i.e., calculation based upon the lung as the critical organ; 3 rads per single study for the whole body, active blood forming organs, lens of the eyes and gonads; 5 rads for other organ per single study limit).

[18F]MeFWAY

While no adverse events have been observed to date in human research with this drug, since fewer than 15 individuals have been injected with [18F]MeFWAY worldwide, even common and serious effects may not be known yet.

Yearly Cumulative Exposure

The radiation exposure table indicated that the total exposure resulting from the study will remain well below the FDA 21 361.1 dose limits for yearly cumulative exposure to research subjects (dose limits of 5 rads per year for whole body, active blood forming organs, lens of the eye and gonads; 15 rads per year for other organs). Each subject will receive up to 4 injections, (up to 2 [11C]DASB and up to 2[11C]CUMI-101 scans). The cumulative exposure due to four injections remains below the FDA annual limits.

Table 3 (Human Data)					

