The dose of radiation will be submitted for approval to the Yale-New Haven Hospital Radiation Safety Committee (Y-NHH RSC). All scans will be done in the presence of medical supervision and trained staff in an institution specifically designed to support imaging studies. In the event of serious medical complications, the PET scan facilities have immediate access to or consultation with specialized medical units at the Yale-New Haven Hospital. Preparation of radiopharmaceuticals and performance of PET scans will be by radiochemists, physicians, and technologists of the Department of Diagnostic Radiology, Yale University School of Medicine. These professionals are qualified by training and experience in the safe use and handling of radiopharmaceuticals.

Subjects will be asked about their previous radiation and those who have had research exposure within the past year will be excluded if cumulative annual exposure (including the present study) exceeds FDA limits. The information on the previous radiation exposure of study subjects will be notified to the study doctor.

No PET studies will be performed on pregnant or potentially pregnant women, as confirmed by pregnancy testing during evaluation and on each scan day before initiation of any scan procedures. If subjects are breastfeeding they will not be able to participate in this research study.

Table 4: Human Dosimetry of [18F]MeFWAY^{101,102}

	mSv,	mSv/MBq		mRad/2.5mCi	
Organ	Female 1.59E-02	Male 1.25E-02	Female	Male	
Adrenals Brain	8.58E-03	5.79E-03	147.25 79.25	116 53.5	

Stony Brook University Human Subjects Committee (IRB)
PSF 2/23/15

Page 28 of 37

IRB# 2012-1826-F PI: [name]				Storiy Brook Universi	пу п
Breasts	7.96E-03	5.99E-03	73.75	55.5	
Gallbladder Wall	2.04E-02	1.68E-02	188.5	155	
LLI Wall	2.32E-02	1.90E-02	215	176	
Small Intestine	1.67E-02	1.44E-02	154.25	133.25	
Stomach Wall	1.18E-02	9.23E-03	109.5	85.5	
ULI Wall	1.58E-02	1.25E-02	146.25	115.75	
Heart Wall	1.25E-02	7.43E-03	115.25	68.75	
Kidneys	3.36E-02	4.95E-02	310	457.5	
Liver	7.54E-02	5.23E-02	697.5	485	
Lungs	2.28E-02	1.32E-02	210.5	122	
Muscle	1.20E-02	9.74E-03	110.75	90	
Ovaries	2.29E-02	N/A	211.5	N/A	
Pancreas	1.51E-02	1.19E-02	139.75	110.25	
Red marrow	1.45E-02	1.22E-02	133.75	113.25	
Osteogenic Cells	1.75E-02	1.29E-02	162	119.5	
Skin	7.68E-03	6.19E-03	171	57.25	
Spleen	1.10E-02	8.85E-03	102	81.75	
Testes	N/A	1.36E-02	N/A	125.75	
Thymus	9.43E-03	7.01E-03	87.25	64.75	
Thyroid	7.64E-03	6.36E-03	70.75	58.75	

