Urinary Bladder Wall*	5.32E-01	4.10E-01	4925	3800	
Uterus	3.67E-02	N/A	340	N/A	
Lens of the Eye	N/A	N/A	N/A	N/A	
Total Body	N/A	N/A	N/A	N/A	

^{*}For the urinary bladder wall, by voiding the bladder at 90 minutes, the radiation dose is expected to decrease to 1.9 Rem for males and 2.46 Rem for females, which is under which is under the 5 Rem single dose limit under the FDA 21 361.1 as mentioned above.

7. Toxicology of Drugs and Radiotracers

[11C]CUMI-101: We have performed the FDA required toxicity study (intravenous) of CUMI-101 (CUNBID-101) in Sprague-Dawley rats sponsored by National Institute of Mental Health (NIMH) in the Toxicology Laboratory of SRI International. We proposed a total human dose of 10 microgram per injection and based on this dose male and female Sprague-Dawley rats (10/sex/group) were given a single iv dose of CUMI-101 at 881 μg/kg (5286 μg/m², 1000 times the human dose, Group 2) or at 88.1 μg/kg (528.6 μg/m², 100 times the human dose, Group 4), or 44.05 μg/kg (264.3 μg/m², 50 times the human dose, Group 5) on Day 1 or twice a day at 440.5 μg/kg/injection (2643 μg/m²/injection, 500 times the human dose; total dose 881 μg/kg and 1000x human dose, Group 3). A control group (10/sex), Group 1, was given a single iv dose of vehicle, 5% ethanol in sterile saline, at an equivalent volume on Day 1. Animals were sacrificed on Day 3 or Day 15 (interim and terminal necropsy, respectively). The following parameters were evaluated for the toxicity evaluation: mortality/morbidity, clinical observations, body weights, food consumption, clinical pathology (hematology and serum chemistry), organ weights, and, at necropsy, macroscopic observation and microscopic histopathology.

Stony Brook University Human Subjects Committee (IRB) PSF 2/23/15

Page 29 of 37

IRB# 2012-1826-F PI: [name]

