5 Rems. For the current proposal, the estimated single study exposure to these organs is below 0.423 Rem (423 mrem). For the maximum number of scans (3), the dose to these organs is below 1.27 Rem (1,270 mrem), which is less than the 5 Rem annual dose limit. As for the other organs, Rems should not exceed 5 Rems for a single dose and 15 Rems for annual and total dose commitment. For the current proposal, the estimated single study exposure to all other organs is below 1.27 Rem (1,270 mrem). For the maximum number of scans (3), the dose to all other organs is below 3.81 Rem (3,810 mrem), which is less than the 15 Rem annual dose limit. Further, the radiation dose is expected to be halved when the participant voids at 90 minutes. The scan will not continue if the participant does not void at 90 minutes.

8. Genetic samples and confidentiality

Samples will be de-identified and coded only with a number; no personal identifying or clinical information is provided to the testing laboratories. Therefore, the risk of a breach in confidentiality is remote.

9. Pregnancy

PI: [name]

Studies involving radiation are contraindicated during pregnancy because of possible risk to the fetus. Women of child-bearing age will be required to have a urine pregnancy test administered on the evaluation day as well as on the day of the PET session prior to scanning. Subjects will not be charged for the pregnancy test. In addition, nursing mothers will also be excluded from the study.

10. Other Risks Associated with Lithium and Lamotrigine Use

Lithium: possible side effects include diarrhea, vomiting, shakiness, drowsiness, slowed thinking, weakening of muscles, difficulty concentrating, acne, weight gain, change in thyroid function and increased urination. Because of the possibility of becoming sleepy, patients will be told to be cautious about driving especially when the medication is started or the dose is raised. Patients will be told to tell their doctor if they develop any of these symptoms. Patients will also be told not to take pain medications such as ibuprofen (Advil, Motrin, or Naproxen [Anaprox]) while on lithium. Diuretics (water pills) such as thiazide or furosemide (Lasix) should not be taken with lithium. Lithium may react with other medications. While taking lithium, before adding another medication patients will be asked to check with their doctor to be sure it is safe.

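### The [11C]CUMI-101 organ doses in the protocol text are about 21 and 11 times those from its own Table 3, and two sections disagree on the [18F]MeFWAY bladder dose

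*Protocol*

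**What the plan says.** **[11C]CUMI-101.** Protocol G.6 names the critical organs: "organ is the testes in males and bladder wall in females for [11C]CUMI-101, and the lungs for [11C]DASB". Under Single Study Limit it gives their dose: "testes in males, bladder wall in females) with the maximum dose of 20 mCi, is 2.4 rem (males) and 1.5 rem (females". Table 3, to which the section refers for CUMI dosimetry, lists 1.52E-03 mGy/MBq for the testes and 1.90E-03 mGy/MBq for the urinary bladder wall. Yearly Cumulative Exposure allows up to two CUMI and two DASB injections. It cites limits of 5 rads a year for gonads, whole body, blood-forming organs and lens, and 15 rads a year for other organs. Citing the exposure table, it says that "the total exposure resulting from the study will remain well below the FDA 21 361.1 dose limits".

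**[18F]MeFWAY.** Table 4 gives the bladder wall 4,925 mRad (female) and 3,800 mRad (male) per 2.5 mCi. Its footnote says: "For the urinary bladder wall, by voiding the bladder at 90 minutes, the radiation dose is expected to decrease to 1.9 Rem for males", and gives 2.46 rem for females. For three scans, G.6 says "the dose to the critical organ would be 5.7 Rad (Rem) for males and 7.38 Rad (Rem) for females". G.7 covers the same tracer but says "the estimated single study exposure to all other organs is below 1.27 Rem (1,270 mrem") and, for three scans, "the dose to all other organs is below 3.81 Rem (3,810 mrem").

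**Use of the figures.** Subjects with research exposure in the past year "will be excluded if cumulative annual exposure (including the present study) exceeds FDA limits" (G.6). The footnotes to the eligibility tables in D.4 apply the same sum, and G.7 repeats the rule for MeFWAY.

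**The concern.** One section gives two values for the same organ, tracer and activity, an order of magnitude apart, and does not say which is current. The organs called critical are among the lower ones in the table. G.7's ceiling for MeFWAY is exceeded by the bladder dose that G.6 and Table 4 report.

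The prior-exposure rule is a sum compared with a limit, and this study's dose is one of its terms. If that term depends on the page used, the same person may be eligible on one reading and ineligible on the other. Committees that review radiation exposure would also be working from inconsistent figures. No endpoint, sample size or analysis is affected.

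**Working it through.** **Conversion.** 20 mCi × 37 MBq/mCi = 740 MBq, and 10 mGy = 1 rem. So dose (rem) = coefficient (mGy/MBq) × 740 / 10.

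**Does the conversion reproduce Table 3?** The cumulative column is for one DASB plus one CUMI scan.
- Testes: (1.52E-03 + 1.74E-03) × 740 × 100 = 241.2 mrem (printed 241), which is 4.8% of 5 rem (printed 4.8).
- Bladder wall: (1.90E-03 + 1.20E-02) × 740 × 100 = 1,028.6 mrem (printed 1,030), which is 6.9% of 15 rem (printed 6.9).
- All 22 organ rows with both coefficients, and the effective dose row, agree with print to within 0.3%. The table's units are therefore not in doubt.

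**CUMI, one 20 mCi scan**

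| Organ | Table 3 | Text | Ratio (range from rounding of the text figure) |
|---|---|---|---|
| Testes | 1.52E-03 × 740 / 10 = 0.112 rem | 2.4 rem | 21.3 (20.9 to 21.8) |
| Bladder wall | 1.90E-03 × 740 / 10 = 0.141 rem | 1.5 rem | 10.7 (10.3 to 11.0) |

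Other numbers of scans do not recover 2.4 and 1.5 rem. In the order testes, bladder wall:
- two CUMI scans: 0.225 and 0.281 rem
- one CUMI plus one DASB: 0.241 and 1.03 rem
- two of each: 0.482 and 2.06 rem

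**Critical organ.** Of the 22 organs with a CUMI coefficient above zero, the testes rank 20th and the bladder wall 14th. The pancreas is highest: 3.20E-02 × 740 / 10 = 2.37 rem. The ranking needs no conversion.

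**Annual testes dose against 5 rem.** DASB from Table 3 is 1.74E-03 × 740 / 10 = 0.129 rem per scan.

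| Scans | Text CUMI + Table 3 DASB | Room left | Table 3 throughout | Room left |
|---|---|---|---|---|
| 2 CUMI + 2 DASB (patient) | 2 × 2.4 + 2 × 0.129 = 5.06 rem (4.96 to 5.16) | about 0 | 2 × 0.241 = 0.48 rem | 4.52 rem |
| 1 CUMI + 1 DASB (healthy volunteer) | 2.4 + 0.129 = 2.53 rem | 2.47 rem | 0.24 rem | 4.76 rem |

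The range for 5.06 comes from the rounding of 2.4 and includes 5, so no excess is demonstrated. The text's CUMI figure alone takes 4.8 of the 5 rem in the patient case.

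**Table 3 at two plus two, highest organs.** Lungs: 2 × (8.60E-03 + 3.28E-02) × 740 / 10 = 6.13 rem. Pancreas: 2 × (3.20E-02 + 3.03E-03) × 740 / 10 = 5.18 rem. Both are under 15 rem.

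**MeFWAY bladder wall.** 2.5 mCi = 92.5 MBq.

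| | Female | Male |
|---|---|---|
| Table 4 coefficient × 92.5 / 10 | 0.532: 4.92 rem (printed 4.925) | 0.410: 3.79 rem (printed 3.80) |
| Halved by voiding (G.6) | 2.46 rem | 1.9 rem |
| Three scans (G.6) | 3 × 2.46 = 7.38 rem | 3 × 1.9 = 5.7 rem |
| G.7 ceiling, one scan | 1.27 rem | 1.27 rem |
| G.7 ceiling, three scans | 3.81 rem | 3.81 rem |
| Post-voiding dose / ceiling | 1.9 | 1.5 |

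G.6 and Table 4 agree with each other; G.7 does not agree with them. For three scans in a woman, the room under the 15 rem limit is 15 − 7.38 = 7.62 rem by G.6, and at least 15 − 3.81 = 11.19 rem by G.7.

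**The case against.** The strongest case accepts the arithmetic and disputes its consequence.

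- **The annual-limit statement cites the exposure table, and it holds on that table.** This is correct. The statement is not contradicted by its stated basis. But it stands just after a text figure that would take 4.8 of 5 rem with CUMI alone, and Table 3 is one of the two sources in conflict.
- **The eligibility conflict is narrow.** It needs a subject with recent research exposure of known dosimetry, and staff who use the sentence and not the table. The near-zero room also combines the text's CUMI dose with Table 3's DASB dose. All of this is fair. Still, nothing says which figure staff should use, and the one-plus-one case shows that the gap is not confined to patients with four injections.
- **G.7's ceiling holds for every MeFWAY organ except the bladder.** This is true: the next highest in Table 4 is the female liver at 0.70 rem, and G.6 gives the bladder separately against its own limits. As written, however, G.7 splits organs into the 3/5 rem group and all others. The bladder falls in the second group, where the ceiling fails. Whether G.7 means its ceiling before or after voiding makes no difference, since both doses exceed it.
- **Radiation committees review the study anyway.** They do, but their review needs figures that agree.
- **Text and table may come from different sources.** This is plausible. G.6 calls the CUMI data human and, in the same sentence, a calculation from baboon data, while Table 3 is headed as human data. That could explain the conflict but does not settle it.

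**Conclusion.** The concern holds. The CUMI doses in the text exceed those from Table 3 by a factor of about 21 for the testes and 11 for the bladder wall, and the two also disagree on the critical organ. For MeFWAY, the post-voiding bladder dose in G.6 is 1.5 (male) to 1.9 (female) times the ceiling in G.7. The result rests on Table 3 being in mGy/MBq at 20 mCi, which its own cumulative and percentage columns confirm.

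No breach of a limit is shown. On Table 3 the permitted two plus two injections stay under every limit cited, and all MeFWAY figures are under 5 rem per scan and 15 rem per year. The documents do not show which figures are right; that is for the sponsor. The point should be corrected because the figures feed an eligibility check and a safety statement.

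**What to change.** From the dosimetry source, the sponsor should:

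1. Reconcile the CUMI testes and bladder wall doses and the named critical organs in G.6 with Table 3, and state whether the data are human or derived from baboons.
2. Reconcile the MeFWAY ceilings in G.7 with G.6 and Table 4, stating whether they include the bladder and whether they apply before or after voiding.
3. Check one further figure at the same time. G.6 gives 2.4 rem as the annual effective dose equivalent for two plus two injections, while Table 3's effective dose row gives 2 × 0.911 = 1.82 rem. The two quantities are not identical, and Table 3 shows zero for the CUMI effective dose equivalent, so the 2.4 cannot be checked from it.
4. Base the annual-limit statement and the prior-exposure check on the reconciled figures, and send them to the radiation committees that already review the study.

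As a matter of presentation, a two-plus-two column beside the correctly labelled one-plus-one column in Table 3 would show the annual totals directly.

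The cost is a recalculation and a correction of text and tables through review already in place. Scans and data collection are unchanged.

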 (8) Current, past or anticipated exposure to radiation, that may include: being badged for radiation exposure in the workplace participation in nuclear medicine procedures, including research protocols in the last year.* (9) A neurological disease or loss of consciousness for 	1. Subjects will undergo a clinical interview, during which they will be asked whether or not they have worked with radioactive substances or have been badged in the past. In addition, they are asked about any prior chemotherapy or radiation treatment. 2. A research assistant will check our database to ensure that the subject has not participated in an imaging study within our department in the past year. Clinical interview
more than a few minutes (10) Medicinal patch that cannot be removed**	Medical history (by a physician),
(11)Patients who are responding satisfactorily to psychiatric medications, because they will not be washed-out for purposes of this study	physical exam. History
(12) A documented history of a lack of response to a trial of adequate dose and duration of both lithium and lamotrigine defined as minimal clinical response to lamotrigine 200 mgs for at least 4 weeks or lithium serum levels of at least 0.8 (or dose >= 900 mgs) for at least 4 weeks	History
(13) Patient is unlikely to be able to tolerate medication washout	Clinical interview
(14) Claustrophobia	Clinical interview

Approved: 12/13/2019
Expiration Date: 12/12/2020
Stony Brook University Human Subjects Committee (IRB)
PSF 2/23/15

Page 12 of 37

IRB# 2012-1826-F PI: [name]

(15) Blood donation within 8 weeks of the start of the study.	Clinical interview
(16) History of a bleeding disorder or are currently taking anticoagulants (such as Coumadin, Heparin, Pradaxa, Xarelto).	History

^{*} Subjects will be eligible if the injected dose and dosimetry of the radiotracer are known and the cumulative annual exposure of the previous study and this study is lower than the annual limit for research subjects defined by the FDA (see below)

HEALTHY VOLUNTEERS:

INCLUSION:		
(1) No lifetime history of Axis I disorders other than	Structured Clinical Interviews I	
specific phobia, social phobia, and/or adjustment	for DSM IV; clinical history and	
disorder.	interview	
(2) Age range 18-70 years.	Interview	
(3) Willing to travel to Yale University for PET	Interview	
scanning.		
EXCLUSION:		
(1) Past or present alcohol/substance abuse or	SCID; Urine drug screen	
dependence except for cannabis use disorders,		

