PSF 2/23/15 Page 18 of 37

The order of [\(^{11}\)C]CUMI-101 and [\(^{11}\)C]DASB administration may be reversed, or subjects may participate in only one scan (either [\(^{11}\)C]CUMI-101 or [\(^{11}\)C]DASB),.

In cases where the subject has a hemoglobin level less than 12 for males and less than 11 for females, we would forgo blood drawing for the [11C]DASB scan except for one sample to be taken at the 50 minute time point, as outlined in the simultaneous estimation (SIME) approach. Likewise, we would forego blood drawing for the [11C]CUMI-101 scan except for one sample at the 60 minute time point. We have recently confirmed that this provides an excellent estimate of the plasma parameters necessary for quantification and modeling of this radioligand. It involves drawing one 12 cc sample off the arterial line at the 50 min post-radioligand injection time point. Therefore, instead of 120 cc being drawn during the DASB scan, we would reduce the blood drawn to 12 cc.

In the case that the two injections are planned but cannot be done on the same day once the PET procedures have been started, subjects may be asked to return on a separate day in order to complete the scans. If the PET procedure has to be rescheduled and placement of another aline is required, subject consent will be sought.

After the acute treatment period, the patients who are on either lithium or lamotrigine will have a second PET scanning session that is identical to the first: up to 20 mCi or less of [11C]CUMI-101 and up to 20 mCi of [11C]DASB. Healthy volunteers will not have follow up scans.

Alternate Location and Tracer for PET Scans

Due to limited availability of PET scans at the Yale PET center, alternative arrangements will be made for subjects at Stony Brook Medicine. In cases where the subject cannot accommodate a trip to the Yale PET center or the Yale PET center cannot accommodate for enough scans due to decreased scan staff, PET/MRI scans may take place at the Siemens Biograph mMR-System located at the Ambulatory Imaging Center using [18F]MeFWAY. Similar to the [11C]CUMI-101 scans being performed at the Yale PET center, [18F]MeFWAY also has the capability to examine 5-HT_{1A} binding. Only bipolar and unipolar patients will be scanned at Stony Brook, when Yale is unable to accommodate the number of scans necessary. Healthy controls will continue to be scanned at Yale PET Center.

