MRI: While there have been no reports of any ill long-term effects caused by magnets of the same or even higher strength, the long-term effects of being placed in a magnet of this strength are unknown. The MRI scanner uses a large magnet to take pictures of the brain and is not associated with any known medical risks, except for persons who have a heart pacemaker, or have metal in their body (e.g. shrapnel or surgical prostheses) which may be affected by the magnet. Patients will be asked to notify us if this is the case. There is also the risk of burns from medicinal patches during the MRI; therefore, subjects will be asked to remove any patches prior to the scanning session. Also, although there are no known risks associated with pregnancy, we will not scan someone who is pregnant. Some people have reported sensations during the MRI scan, such as "tingling" or "twitching" (or, very rarely, a painful sensation), which are caused by changes in the magnetic field that can stimulate nerves in the body. If the subject experiences sensations and feels uncomfortable, the MR technologist will stop the scan immediately. Occasionally, some people experience nervousness or

IRB# 2012-1826-F PI: [name] Stony Brook University Human Subjects Committee (IRB)
PSF 2/23/15

PSF 2/23/15 Page 25 of 37

claustrophobic feelings due to the scanner's small space. Despite these sensations, in our experience, no one has had sensations from the scanning that did not stop as soon as the scanning stopped. The MRI scan is not painful, but having to lie still in the enclosed space of the scanning table is uncomfortable for some people.

fMRI: The risks associated with the fMRI due to the magnet strength are exactly the same as the risks associated with the MRI.

6. Radiation Exposure (PET)

The Yale-New Haven Hospital Radiation Safety Committee (RSC) will review the use of radiation in this research study, and no subjects will be enrolled until RSC approval is obtained. This research study involves exposure to radiation from [11C]CUMI-101 and [11C]DASB PET scanning. This radiation exposure is not necessary for medical care and is for research purposes only.

The targeted amount of radiation an individual subject will receive in this study per year is from up to 2 injection(s) of \leq 20 mCi from [11 C]CUMI-101 and from up to 2 injection(s) of \leq 20 mCi from [11 C]DASB plus transmission scans.

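### Table 3's yearly radiation columns cover one scanning session, half of what its own coefficients give for patients with two, and the totals in the text do not agree with the table

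*Protocol*

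**What the plan says.** Section D.5 (PET Studies) states that after acute treatment "the patients who are on either lithium or lamotrigine will have a second PET scanning session that is identical to the first", and that "Healthy volunteers will not have follow up scans". Section G.6 (Radiation Exposure) sets the yearly maximum at two CUMI-101 and two DASB injections of up to 20 mCi each.

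G.6 then gives dose figures in three places:

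- The opening text says the yearly maximum "is equal to an effective dose equivalent of 2.4 rem for a total of 2 injection(s") of each tracer, and compares this with an annual effective dose limit of 5 rem.
- Under Single Study Limit, one 20 mCi CUMI-101 injection is said to deliver 2.4 rem to the testes or 1.5 rem to the bladder wall.
- Under Yearly Cumulative Exposure, the radiation exposure table is cited as showing that the whole study stays well under the yearly limits (5 rads for whole body, marrow, lens and gonads; 15 rads for other organs). The paragraph ends: "The cumulative exposure due to four injections remains below the FDA annual limits". The table for these tracers, Table 3, heads its cumulative columns as one DASB plus one CUMI.

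The eligibility footnotes in D.4 admit a person with earlier research exposure if the "cumulative annual exposure of the previous study and this study is lower than the annual limit for research subjects defined by the FDA". G.6 repeats the rule after Table 3. Neither place says what number to enter for the present study.

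**The concern.** A column labelled per year, and cited in support of a four-injection total, counts two injections. A reader who takes the yearly figure or the percentage of limit from Table 3 gets half of what the table's coefficients imply for a patient scanned before and after treatment. The text offers a different total, in a different dose quantity, that the table does not yield. Its single-injection organ doses for CUMI-101 are also far from the table's.

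The protocol therefore has no single, traceable figure for what a patient receives from this study. The prior-exposure rule needs such a figure, because it adds the study's dose to what the person has already had.

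**Working it through.** **Inputs.** Activity per injection: 20 mCi × 37 = 740 MBq (G.6). Coefficients from Table 3, with CUMI-101 first and DASB second: effective dose 5.33E-03 and 6.98E-03 mSv/MBq; effective dose equivalent 0.00 and 8.01E-03 mSv/MBq; lungs 8.60E-03 and 3.28E-02 mGy/MBq; testes 1.52E-03 and 1.74E-03 mGy/MBq; bladder wall for CUMI-101 1.90E-03 mGy/MBq. Conversion: 1 mSv or mGy = 100 mrem.

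**Step 1: reproduce the printed column.** Effective dose for one injection of each: (5.33E-03 + 6.98E-03) × 740 = 9.11 mSv = 911 mrem, and 911/5,000 = 18.2%. Both match Table 3. All 25 numeric rows reproduce within 1% on this basis, so the arithmetic is sound for one session.

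**Step 2: two sessions.**

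| Row | 1 + 1 (printed) | 2 + 2 | Annual limit | % of limit at 2 + 2 |
|---|---|---|---|---|
| Effective dose | 0.911 rem | 1.82 rem | 5 rem | 36.4 |
| Lungs | 3.06 rem | 6.13 rem | 15 rem | 40.8 |
| Pancreas | 2.59 rem | 5.18 rem | 15 rem | 34.6 |
| Red marrow | 0.303 rem | 0.61 rem | 5 rem | 12.1 |
| Testes | 0.241 rem | 0.48 rem | 5 rem | 9.6 |

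Lungs are the highest row relative to the limit. No row reaches its limit after doubling.

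**Step 3: try to rebuild the 2.4 rem.**

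- Effective dose equivalent, 2 + 2: 2 × (0.00 + 8.01E-03) × 740 = 11.9 mSv = 1.19 rem.
- Effective dose, 2 + 2: 1.82 rem.
- Effective dose plus four transmission scans at 2.5 mrem each: 1.83 rem.

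None gives 2.4. Four times the DASB dose equivalent is 4 × 0.593 = 2.37 rem, which would round to 2.4 if CUMI-101 had been given DASB's value, but the documents do not say that this was done.

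**Step 4: single-injection CUMI-101 organ doses.**

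- Testes from Table 3: 1.52E-03 × 740 = 1.12 mGy = 0.11 rem; the text says 2.4 rem.
- Bladder wall from Table 3: 1.90E-03 × 740 = 1.41 mGy = 0.14 rem; the text says 1.5 rem.

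If the text's testes figure stood, four injections would give 2 × 2.4 + 2 × (1.74E-03 × 740)/10 = 4.8 + 0.26 = 5.06 rem, above the 5 rem annual gonad limit. Table 3 gives 0.48 rem for the same four injections.

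**Step 5: room for prior exposure under 5 rem.**

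- Printed column: 5 − 0.911 = 4.09 rem.
- Table 3 at 2 + 2: 5 − 1.82 = 3.18 rem.
- Stated total: 5 − 2.4 = 2.60 rem. This is dose equivalent, so it is not strictly comparable with the other two.

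As an assumed example, a patient with 3.5 rem of earlier exposure would total 4.41 rem with the printed figure, and 5.32 rem with Table 3 at 2 + 2.

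**The case against.** The strongest reply is that nothing is miscalculated. The column states its basis, every row reproduces, and it is correct for the 38 healthy volunteers among the 86 planned subjects. G.6 openly states the four-injection maximum. Its assurance about four injections survives doubling on Table 3's coefficients. The 2.4 rem and the 911 mrem are also different quantities, so their inequality is not in itself a contradiction. All of this stands, except that the assurance does not survive for the testes if the text's single-injection figure is used.

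A reader might infer that Table 3's yearly column is the number used in the eligibility check, so that patients are being admitted on half their dose. The documents do not say so: the rule names no table and no figure. The only number labelled as the yearly study maximum is the 2.4 rem, which leaves the least room of the three totals. Nor do they support saying that the radiation committees were shown halved percentages, since the submission is not among the documents. Counting one session also does not explain the 2.4 rem, because doubling does not produce it.

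The practical reach is narrow. Decisions could differ only for patients with roughly 2.6 to 4.1 rem of research exposure in the preceding year, which is more than this whole study delivers by its own effective-dose or dose-equivalent totals. The documents do not say how often that occurs.

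**Conclusion.** The point holds in a limited form. As a yearly figure for patients with two full sessions, Table 3's cumulative columns are wrong as written and are half of what the table's own coefficients give. Separately, the 2.4 rem study total and the two single-injection CUMI-101 organ doses in the text cannot be reconciled with the table. The organ-dose gap is about 21-fold for testes (2.4/0.1125) and 11-fold for bladder wall (1.5/0.1406).

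This does not show that the study breaches a limit. On Table 3's coefficients it does not, and only the text's testes figure would take four injections past the gonad limit. Which set of figures is right cannot be settled from the documents, so doubled Table 3 should not be read as the true dose.

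The calculation assumes the maximum 20 mCi at every injection and both tracers at both sessions. Patients who have only one tracer would receive less. Those scanned with [18F]MeFWAY fall under Table 4 and are not covered here.

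**What to change.** Add a two-session column (2 DASB + 2 CUMI-101) with percentages of limit to Table 3 for patients, and keep the one-session column, labelled for healthy volunteers. Reconcile the opening text of G.6, the Single Study Limit paragraph and Table 3, stating for each figure the dose quantity and its dosimetry source, and resolve the 0.00 entry for CUMI-101 effective dose equivalent. In the eligibility footnotes and the matching paragraph of G.6, name the single study total per group to be added to prior exposure. The radiation safety committees should confirm which figures stand.

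The cost is a table and text amendment, and possibly a rare patient with high earlier research exposure becoming ineligible.
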